6.0 Study Treatment or Procedures

- Completion of the Staging MRI with contrast is mandatory for all patients.
- Minimum and maximum (1-2) dominant intraprostatic tumor foci are suggested on MRI during screening
- Visualization of the urethra on CT scan for treatment planning will be accomplished through fusion of pelvic MRI with CT simulation images.
- Baseline testosterone

- In addition to standard of care IPSS and SHIM questionnaires, EPIC, EQ5D, and Utilization of Sexual Medications/Devices Supplement will be obtained at baseline, and 6, 12 and 24 months post end of radiation therapy.

6.1.1 Description of Radiation Therapy

Radiation treatment will be delivered using Elekta S Agility, LINAC-based technology (SBRT). Prior to SBRT 3-5 fiducial markers will be placed in the prostate for image guidance during radiation therapy. Fiducial marker placement will be conducted using standard of care FDA approved ultrasound guidance device and will incorporate findings from MRI image sets to guide the selection of biologic target volumes suggested on imaging to represent tumor burden within the prostate. If eligible, patient may also have a hydrogel spacer placed to maximally spare the rectum, as per standard of care. At least 1 week will elapse between fiducial marker and hydrogel spacer placement and treatment planning simulation to allow for fiducial settling and any potential for migration. Using a LINAC-based SBRT system, the technique of motion control will be abdominal compression and /or rectal balloon, combined with 4D CT simulation. This information related to treatment and treatment planning will be recorded and processed in the UHCMC Seidman Cancer Center Department of Radiation Oncology password protected electronic medical record per institutional policy.

Imaging the Prostate

All patients will undergo a Serum Creatinine clearance study prior to MRI exams. Patients who are unable to undergo a staging MRI scan with contrast during screening will not be eligible for the study. Prior to radiation therapy, all patients will have a staging 3T MRI (utilizing a body coil) of the pelvis to include standard (T2 weighted) and multiparametric MRI sequences (to include Dynamic Contrast Enhanced and Diffusion Weighted scans or mpMRI) with gadolinium contrast. Axial, sagittal and coronal MRI scans are required for all MRI scans.

CT and MRI Treatment Planning Simulation

Each patient will have a treatment planning simulation prior to delivery of SBRT at least 1 week following the insertion of radio-opaque fiducial markers implanted in the prostate for target localization and daily set up during fractionated dose delivery. A custom made immobilization device consisting of a whole body vac bag and vacuum wrapping (Medical Intelligence BodyFix) will be made for every patient. A CT scan with and without contrast of the pelvis will be performed with the immobilization device in place. If the patient is not a candidate for CT contrast, non-contrast CT will be performed. Treatment planning CT scans must take into account the respiratory motion. A 4DCT or combination of end-inspiration and end-expiration CT scans will be taken. A treatment planning MRI (with contrast is preferred and using standard MRI and mpMRI sequences as described above for the staging MRI) will be acquired following placement of fiducial markers and prior to delivery of SBRT. A rectal balloon may be used during simulation and treatment, as tolerated by each subject.

Dose Specifications

Radiation will be delivered in to 29.25 Gy in 3 fractions (9.75 Gy per fraction) to involved sub-volume/s of the prostate using VMAT by the Synergy S with Agility collimator (Elekta, Stockholm, Sweden and Atlanta, GA) as focal therapy. Dose escalation to organs-at risk surrounding the prostate target volume is not allowed. Dose constraints of normal tissues surrounding the target will be set to limit toxicity. Although this three fraction SBRT regimen is novel, the tolerance levels selected for the normal organs are consistent with Radiation Therapy Oncology Group (RTOG) protocol RTOG 0938

“A randomized phase II trial of hypofractionated radiotherapy for favorable risk prostate cancer” (<http://www.rtog.org/ClinicalTrials/ProtocolTable/StudyDetails.aspx?study=0938> accessed 12/09/2013) and selected to provide the minimal Biological Equivalent Dose (BED) or Equivalent Dose in 2 Gy fractions (EQD2) felt to be required at a high dose per fraction to provide a high likelihood for tumor control as noted above in the concluding paragraph of the introduction (page 9).

This protocol requires the use of SBRT that uses inverse treatment planning (dose specifications are provided below in further detail). It is thought that SBRT treatment plans and delivery for this pilot series may be achievable without increase in normal tissue toxicity compared to whole organ treatment using either SBRT or HDR brachytherapy as defined above. If a patient is determined to have failed therapy using acceptable clinical standards, such as the Phoenix definition (a rise in PSA following nadir of 2 ng/mL) or biopsy proven locally recurrent or persistent disease, the patient may be offered other curative therapy or therapies off study, depending on the patient’s clinical status and intent to treat.

Dose Coverage

The isodose line used for the prescription dose should cover a minimum of 95% of the PTV. This will be recorded in the Department electronic medical record for each patient.

Minimum Dose

The minimum dose within the PTV to a point that is 0.03 cc in size must be $\geq 95\%$ of the prescribed dose. This will be recorded in the electronic medical record for each patient.

Critical Structures

Critical Organ Dose-Volume Limits

The normal tissue volume to be contoured will include bladder, rectum, bilateral femora (to the level of ischial tuberosity), seminal vesicles, penile bulb, neurovascular bundles, skin, and urethra. The normal tissues will be contoured and considered as solid organs rather than contouring the bladder and rectal walls. The bladder should be contoured from its base to the dome. The rectum should be contoured from the anus (at the level of the ischial tuberosities) for a length of 15 cm or to the rectosigmoid flexure. This generally is below the bottom of the sacroiliac joints. The tissue within the skin and outside all other critical normal structures and PTVs are designated as unspecified tissue. These data will be recorded in the electronic medical record for each patient.

Supportive Measures

Urinary

Symptomatic urinary medicines, (e.g. tamsulosin) are allowed at the discretion of the treating radiation oncologist or urologist.

Bladder

Patients will be asked to have a full urinary bladder both during simulation and treatment. Consistent bladder filling procedure should be used for an individual patient for simulation and for each treatment. Bladder filling may be achieved by asking patients to drink 16-24 oz of water or other fluid 2-3 hours prior to treatment and to not urinate between this time and treatment as they are able.

Bowel

Patients will be advised to adhere to a low gas, low motility diet commencing one day prior to the treatment. One tablespoon of Milk of Magnesia will be taken the night before the simulation and the

night before each treatment. One Fleet's enema will be administered 2-3 hours before the simulation and each treatment. Rectal balloons may be used when patients tolerate, both for simulation and during treatments at the discretion of the Radiation Oncologist.

Supportive measures will be recorded in the usual fashion in the electronic medical record.

SBRT Dose Constraints

Organ	Volume	Dosimetry Parameters
		Dose (Gy)
Prostate (PTV)	Maximum point dose (0.03cc)	≤ 31.298 Gy 107% of prescription dose *
	Minimum dose received by 95% of PTV	≥ 29.25 Gy 100% of prescription dose
	Minimum dose received by PTV	≥ 27.79 Gy 95% of prescription dose
Rectum	Maximum point dose (0.03cc)	≤ 30.71 Gy 105% of the prescription dose
	Less than 3 cc	< 27.79 Gy 95% of prescription dose
	90% rectum	≤ 26.325 Gy 90% of prescription dose
	80% rectum	≤ 23.40 Gy 80% of prescription dose
	50% rectum	≤ 14.625 Gy 50% of prescription dose
Bladder	Maximum point dose (0.03cc)	≤ 30.71 Gy 105% of prescription dose
	90% Bladder	≤ 26.325 Gy 90% of prescription dose
	50% Bladder	≤ 16.5 Gy 50% of prescription dose
Penile bulb (recommended)	Maximum point dose	No more than 100% of prescription dose
	Less than 3 cc	15.795 Gy 54% of prescription dose
Femoral heads Skin (recommended)	Less than 10 cc cumulative (both sides)	15.795 Gy 54% of prescription dose
	Maximum point dose	23.69 Gy 81% of prescription dose
Urethra dose		≤ 31.298 Gy * 107% of prescription dose

*Visualization of the urethra would be required to confirm urethral dose is ≤31.298 Gy – 107% of prescription dose where the max point dose (0.03cc) within the PTV exceeds 31.298 Gy – 107% of prescription dose. Prescription and treatment notes will be recorded in the electronic medical record.

Technical Factors

Stereotactic Targeting and Treatment

This protocol will require treatments to be performed with an image-guided technique with the use of a 3-D coordinate system defined by 3D sub-volume/s of the prostate using VMAT by the Synergy S Agility collimator (Elekta, Stockholm, Sweden and Atlanta, GA). A computerized method for image registration is required for determination of the patient shift information. Serial MRI images with parametric sequencing will be used both to evaluate intra fraction response and post therapy response. The intrafraction image (between the second and third fraction) will be evaluated for yield in intra-therapy response, that may be useful future in clinical applications such as in MRI-Linac based adaptive radiotherapy planning. Post therapy serial MRI will also be used to evaluate radiographic determined response to therapy, versus pre and mid treatment scans and as compared to clinical features such as PSA follow-up.

All available image sets will be co-registered using clinical software such as MIM Maestro (MIM software, Cleveland, OH) and PercuNav (Invivo, Gainsville, FL) and/or evaluated using our available in-house developed software for image registration verification, as is customary for clinical cases. Imaging data will thus be transferred to our Linac based treatment planning system Pinnacle, Philips Medical Systems (Cleveland, OH) for SBRT delivery. We will also use 3D cone-beam kV CT for alignment of *in-vivo* fiducials to track and adjust for internal target motion detection.

As previously described (6.1 Description of Radiation Therapy) a minimum of three and maximum of five radio-opaque fiducial markers will be inserted in to the prostate for use in fractionated dose target positioning during SBRT (delivered in three fractionated doses on 3 different days, typically every other day). At least one fiducial marker for treatment planning will be guided to a prostatic region reported on mpMRI to be highly suspicious for tumor burden.

For patients who have not previously received a targeted biopsy (in-gantry MRI or US-MRI fusion), during this fiducial marker placement procedure, and just prior to needle insertion to place the fiducial marker, a guided biopsy will be targeted to the location of disease suggested by mpMRI using FDA approved devices for image guided biopsy procedures. An FDA approved sterile surgical needle will be introduced either transrectally or transperineally through which the biopsy needle will pass. Following extraction of tissue sample, a fiducial marker will be placed in each of 3-5 biopsy cavities and recorded for spatial *in-vivo* orientation with to the anatomic and functional image sets (US, CT, MRI and mpMRI).

If additional mapping biopsies are necessary, other sextant regions of the prostate reported as normal by screening MRI will be biopsied as is typical for a mapping biopsy procedure to improve disease staging and localization of true positive disease during the screening procedure. Thus, a total of 12 to 15 biopsies will be obtained from each patient for screening eligibility to aid in a determination of likelihood that disease is not multifocal and to enable delivery of focal partial organ therapy. Each biopsy site will be tracked using a combination of permanent and virtual fiducial markers. Virtual markers will be electronically tracked in the regions suggested to be negative for the presence of disease on imaging at the sites of all other sextant biopsy locations using the biopsy needle tip as a temporary fiducial imaged by ultrasound at the time of biopsy and fused back to the mpMRI and planning CT scan if the patient goes on to be treated on protocol.

It should be noted that the permanent fiducial markers placed for screening would not preclude prostatectomy, or could be used for directing radiotherapy if the patient is found to be ineligible for

partial prostate treatment based on more extensive pathology being found on the screening biopsy. Conversely, should the patient elect to remain in active surveillance despite qualifying for the protocol, the fiducials would serve to help direct subsequent biopsies required for active surveillance. Inserted permanent fiducial markers will satisfy the following requirements for prostate cancer: (1) good radiographic visibility on kV imaging/diagnostic Xrays, (2) minimal distortion of delivered dose, (3) minimal artifacts on MRI and CT images used for treatment planning, and (4) minimal migration during treatment. Temporary markers (biopsy needle tip tracking) will be used to track mapping biopsy locations (≤ 12 additional sites) and all biopsy locations will be recorded and tracked for *in-situ* position and for subsequent correlation to pathology findings and sequential MRI scans. Individual biopsy tissue samples will be labeled and processed by the institution's clinical pathology laboratory for prostate biopsy reporting.

Three D (3D) mapping will be used with SBRT using cone beam CT (CBCT). Doses reported for kV cone beam CT on the Elekta Synergy machine are in the range of < 3 cGy per image Alaei (2010). The doses for 3D imaging systems are anticipated in this study to be around 12 cGy per fraction assuming 4 CBCT's daily during treatment cGy. Thus one may assume that the total dose delivered daily may actually be at least 9.87 cGy when taking into account the prescribed dose of 9.75 Gy and the 12 cGy daily IGRT. This would yield a total BED of 273.15 for an alpha beta of 1.2 allowing us to reach the desired minimal BED of 268 suggested by Martinez (2011).

Localization

We will use a set-up CBCT, as well as repeat CBCT after every 3.25 Gy and following completion of therapy daily to assess intrafraction prostate organ motion. One goal of the project will be to use these data to assess the need for continuous IGRT such as that achievable with MRI Linac based SBRT applications. The Hexapod couch will be used to correct for rotation using the fiducial markers for each IGRT image set during treatment. A minimum of 4 IGRT CBCT's will be acquired daily as initial setup and after every 3.25 Gy has been delivered to assess intrafraction prostate motion. At the discretion of the radiation oncologist/physicist, monitoring of intrafraction motion may be required more frequently.

Imaging studies for staging, treatment planning and response to therapy monitoring

Multiparametric and Magnetic Resonance Imaging (mpMRI)

Prior to radiation therapy, all patients will have standard of care staging and treatment planning MRI's of the pelvis, with contrast unless clinically contraindicated, using standard morphologic imaging sequences, per institutional standard of care imaging protocols for anatomic detail and localization. Additional functional mpMRI sequences will also be acquired and evaluated to enable morphologic and/or quantification of various tissue parameters as are routinely ordered prior to radiation therapy. The duration of the entire mpMR imaging procedure (patient on the scanner table) will be no longer than a total of 90 minutes, which is within the range for a standard single diagnostic MRI scan. Quantitative MRI data may include analysis of some or all of the following parameters:

Diffusion weighted imaging (DWI):

- Measurement of b-value assesses different levels of diffusivity within tumor tissue and normal tissue.
- Apparent diffusion coefficient (ADC) will be calculated as a quantitative measure from multiple b-values by measurement of ROI in the target lesion.

Dynamic contrast enhanced MRI (DCE-MRI):

- Typical quantitative parameters will be obtained describing tissue enhancement pattern and perfusion, contrast agent exchange rates of tissues and distribution of contrast between the various tissue spaces using standard evaluation models.
- Quantitative assessment will be performed with post processing techniques as commercially available as well as post processing software under investigation or development to demonstrate feasibility with currently available and future techniques.

These sequences will be recorded for virtual comparison to the standard MRI sequences to determine if the investigational functional data correlates with histopathology data, and to determine if these data would have changed the radiation therapy contouring and dose delivery. Any change in treatment planning due to functional MRI versus standard sequences alone will be recorded, and evaluated for utility in the determination of tumor response to therapy.

Target Delineation

All clinically relevant radiologic images will be transferred to the Radiation Oncology Pinnacle (Philips, Cleveland, OH) treatment-planning system. Using the various MRI sequences and the CT image data sets, a composite gross tumor volume (GTV) will be generated. The focal GTV will be contoured and approved by the attending radiation oncologist and urologist. The 4D CT will be fused with the treatment planning CT and an internal target volume (ITV) will be generated. The location of tumor foci from each positive biopsy core will also be segmented and expanded by 5mm to add to the PTV along with imaging data sets. An additional 0.3-0.5 cm margin will be placed around the image data set ITV to generate a final PTV to account for set-up variation. The use of abdominal compression may be used to decrease the volume of ITV since there is no real-time target tracking. Surrounding normal structures, including the rectum, small bowel, bladder, femora, seminal vesicles, penile bulb, and skin will be contoured. Skin is defined as a 0.5 cm concentric ring beneath the skin.

Mid Treatment and Post SBRT (MRI) with multiparametric sequences (mpMRI)

Each subject will be offered up to 4 additional MRI scans: 1 during therapy (between the 2nd and 3rd fractionated treatments), at 6 months following the end of radiation therapy, and again at 12 and 24 months. All mpMRI will be requisitioned in the same manner as described above (Staging MRI) as described above at page 16 (6.1 Imaging the Prostate), with the exception that contrast with gadolinium is preferred. If patients are unwilling or clinically unable to undergo contrast or have all follow-up MRI scans, the patient will remain on study and followed for PSA response and toxicity outcomes.

Computed Tomography (CT)

CT will be fused with MRI scans and used as a primary image platform for treatment planning. It is preferred that CT with contrast be acquired, unless clinically contraindicated. The simulation should be performed in the supine treatment position, in the custom made immobilization device, with the fiducial markers and rectal balloon in place (where utilized). Axial cuts of 2.0 mm or less will be acquired throughout the pelvis and prostate from the top of the iliac crests superiorly to the perineum inferiorly.

Contrast

CT scans with and without IV contrast are required, unless contraindicated. Dose calculations will be based on the non-contrast study, and the contrast study if obtained will be used to delineate prostate and surrounding organs at risk including bladder.

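### The 50%-bladder dose limit contradicts itself: 16.5 Gy is labelled 50% of a 29.25 Gy prescription, but 50% is 14.625 Gy and 16.5 Gy is 56.4%

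*Combined protocol and SAP*

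**What the plan says.** Section 6.1.1 (Dose Specifications) prescribes 29.25 Gy in three fractions of 9.75 Gy. Its SBRT Dose Constraints table lists limits for the target and the surrounding organs, nearly all as a dose in Gy with the matching percentage of the prescription. The entries that matter here are:

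- Dose to 95% of the PTV: "≥ 29.25 Gy 100% of prescription dose". This fixes the table's 100% base.
- 50% of the rectum: "≤ 14.625 Gy 50% of prescription dose".
- Bladder maximum point dose: "≤ 30.71 Gy 105% of prescription dose".
- 90% of the bladder: "≤ 26.325 Gy 90% of prescription dose".
- 50% of the bladder: "≤ 16.5 Gy 50% of prescription dose".

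On the purpose of these limits, Dose Specifications says: "Dose constraints of normal tissues surrounding the target will be set to limit toxicity". It also says that "the tolerance levels selected for the normal organs are consistent with Radiation Therapy Oncology Group" protocol 0938, which is not part of the documents. Some rows of the table are marked as recommendations only; the bladder rows are not.

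**The concern.** The 50%-bladder row states one limit in two forms that cannot both hold for a 29.25 Gy prescription. The same table gives a different dose, 14.625 Gy, for the same 50% label in the rectum block. No footnote or other section gives the bladder row a different base or says whether the Gy figure or the percentage governs.

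This is a working limit for inverse planning in a regimen that the protocol itself calls novel. A plan can comply by the Gy figure and breach by the percentage, so two planners, or a planner and an auditor, could classify it differently. The printed Gy figure is the looser of the two. The bladder also matters to the aims of the trial: the EPIC urinary score is a co-primary endpoint in Section 9.0, and Section 10.2 names acute and late toxicity as the primary goal.

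**Working it through.** **Inputs.** Prescription: 3 × 9.75 = 29.25 Gy (Section 6.1.1, Dose Specifications; also Sections 3.1 and 4.3). Stated limits and percentages: the SBRT Dose Constraints table.

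**Formulas.** Expected limit = stated percentage × 29.25 Gy. Actual percentage = stated Gy ÷ 29.25.

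**Every row that gives both values:**

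| Row | Stated Gy | Stated % | Expected Gy | Stated − expected |
|---|---|---|---|---|
| PTV, maximum point | 31.298 | 107 | 31.2975 | +0.0005 |
| PTV, 95% of volume | 29.25 | 100 | 29.25 | 0 |
| PTV, minimum | 27.79 | 95 | 27.7875 | +0.0025 |
| Rectum, maximum point | 30.71 | 105 | 30.7125 | −0.0025 |
| Rectum, under 3 cc | 27.79 | 95 | 27.7875 | +0.0025 |
| Rectum, 90% | 26.325 | 90 | 26.325 | 0 |
| Rectum, 80% | 23.40 | 80 | 23.40 | 0 |
| Rectum, 50% | 14.625 | 50 | 14.625 | 0 |
| Bladder, maximum point | 30.71 | 105 | 30.7125 | −0.0025 |
| Bladder, 90% | 26.325 | 90 | 26.325 | 0 |
| **Bladder, 50%** | **16.5** | **50** | **14.625** | **+1.875** |
| Penile bulb, under 3 cc | 15.795 | 54 | 15.795 | 0 |
| Femoral heads, under 10 cc | 15.795 | 54 | 15.795 | 0 |
| Skin, maximum point | 23.69 | 81 | 23.6925 | −0.0025 |
| Urethra | 31.298 | 107 | 31.2975 | +0.0005 |

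Fourteen of the 15 pairs are reproduced to within 0.0025 Gy. The 50%-bladder pair is not: 16.5 ÷ 29.25 = 56.4%.

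**Alternative explanations tested.**

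- *Rounding.* The largest rounding difference elsewhere is 0.0025 Gy; this one is 1.875 Gy.
- *A separate base for the bladder.* The other two bladder rows imply 26.325 ÷ 0.90 = 29.25 Gy and 30.71 ÷ 1.05 = 29.248 Gy.
- *Imaging dose included.* Section 6.1.1 adds 12 cGy of cone-beam CT dose per fraction: 3 × (9.75 + 0.12) = 29.61 Gy. Half of that is 14.805 Gy, and 16.5 ÷ 29.61 = 55.7%.
- *Another prescription.* 16.5 Gy is 50% of 16.5 ÷ 0.50 = 33.0 Gy, a total dose that the protocol does not prescribe.
- *A broken table.* The Gy figure and the percentage stand together on one line and the neighbouring rows read cleanly, so damage in the PDF reading is unlikely.

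**Size of the gap.** 16.5 − 14.625 = 1.875 Gy. Relative to the lower figure: 1.875 ÷ 14.625 = 12.8%. Relative to the prescription: 1.875 ÷ 29.25 = 6.4 percentage points. Per fraction: 16.5 ÷ 3 − 14.625 ÷ 3 = 5.5 − 4.875 = 0.625 Gy.

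**Which plans are affected.** Writing D50 for the dose to 50% of the bladder: at or below 14.625 Gy a plan passes both halves of the limit; above 16.5 Gy it fails both; only between the two do the halves give different answers.

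**The case against.** The arithmetic is not in dispute. The strongest objection is that it shows an inconsistency without showing which half is wrong. The tolerances are tied to an external protocol that the documents do not reproduce, so 16.5 Gy could be a deliberate absolute limit with a mistaken percentage beside it. The column is headed in Gy, which gives some reason to treat the Gy figure as the operative one. The statement that "Dose escalation to organs-at risk surrounding the prostate target volume is not allowed" is a general prohibition and does not choose between two candidate limits.

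Much of this stands. The intended value cannot be proved from the documents, and the ban on escalation is weak support for the lower figure. The column heading is not decisive either, since one penile-bulb entry under it gives only a percentage. The objection therefore bears on the choice of correction; the contradiction itself remains.

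A second objection is that the practical reach may be small. Only part of the prostate is treated, the bladder is kept full, and it is contoured whole, so half of its volume may seldom receive a dose in the affected band. That is plausible, but it is inference: the documents report no D50 values. It is also fair that the other bladder limits are internally consistent, and that the protocol names no specific consequence for missing this row.

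**Conclusion.** The concern holds. The 50%-bladder limit is wrong as written: one of the 15 Gy/percentage pairs in the table is inconsistent, by 1.875 Gy. The conclusion rests only on the 29.25 Gy prescription and on the table's own 100% row. Which figure was intended remains open, although 14.625 Gy agrees with the rest of the table and is the more protective reading.

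The consequence is confined to plans with bladder D50 above 14.625 Gy and up to 16.5 Gy, and nothing in the documents shows that such a plan exists. No endpoint definition, sample-size figure or analysis depends on the row. Because it is an operative organ-at-risk limit in a trial that assesses urinary toxicity, it should be corrected, but it does not threaten the trial's conclusions.

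**What to change.** Change the 50%-bladder row to a limit of 14.625 Gy, labelled 50%. If the sponsor confirms from the source of the tolerances that 16.5 Gy was intended, keep that figure and relabel it 56.4%. Either change removes the contradiction; the lower figure is the better default because it protects the bladder more.

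Once the limit is settled, check bladder D50 in the treated plans against it and record any plan that exceeds it.

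The cost is one table cell and a review of about 12 plans (Section 4.2 anticipates 12 enrolled). The bladder is already contoured for every patient under Critical Organ Dose-Volume Limits. The protocol does not say that D50 itself is tabulated, so it may have to be read from the stored plans. No new patient data are needed.
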